5.7.1 Dispensing of Study Drug

EDP-938 and placebo must be dispensed by a licensed investigational pharmacist or other authorized site staff with appropriate training. [REDACTED]

5.7.2 Treatment Compliance

The subject will be instructed to bring all study drug (including empty bottles) to the site on Day 3, Day 5, and EOS Visit (for subjects who discontinue study drug or the study early). Both accountability and study drug compliance, including tablet counts and the electronic dosing record (or back-up paper diary as applicable) completed by the subjects, will be reviewed at each study site visit as indicated in the SoA (Appendix 1). The number of tablets will be counted, and

the site staff will ask the subjects why any doses were missed, if applicable. Any potential reasons for lack of compliance with dosing will be monitored and followed up by the site staff. Compliance assessment may be completed at the study site or by a study nurse via a home visit, if feasible; refer to the SPM for details.

The time and date of doses of study drug taken at the study site should be recorded by site staff. From Day 1, subjects will electronically record the time and date that each dose is taken. In case the subject is unable to complete any assessments or recordings into the device for technical reasons, the subject will also be provided with a paper diary(ies) as a back-up.

For any subject considered to demonstrate continued noncompliance of study drug dosing despite continued educational efforts, the Investigator should contact the [REDACTED] or the Sponsor's Medical Monitor to discuss possible discontinuation of the subject from the study.

5.8 Concomitant Medications

All subjects enrolled in the study must abstain from taking any prohibited medications through the end of the study (see [Section 5.9](#)).

If RSV symptoms occur, such as fever or headache that require symptomatic relief during the study, then subjects may take acetaminophen at a dose of 3000 mg/day or less. Acetaminophen will be permitted only for the relief of fever or pain. From Day 1, subjects will electronically record the date and time of any acetaminophen use. In case the subject is unable to complete any recordings into the device for technical reasons, the back-up paper diary may be completed by subjects [REDACTED]

For subjects with physician-diagnosed asthma, current GINA Steps 2, 3, or 4 treatment will be allowed as long as the dose is stable for at least 4 weeks prior to Screening. The GINA treatment guidelines (ie, main report and pocket guide) may be accessed at: <https://ginasthma.org/reports/>. Administration of more than two maintenance asthma therapies or theophylline preparations will not be allowed for study participation.

For subjects with physician-diagnosed COPD, short-acting bronchodilators (as required) are permitted. No more than two maintenance therapies are permitted. Receipt of theophylline, roflumilast, maintenance oral corticosteroids, or long-term oxygen therapy (defined as prescribed for 12 or more hours per day) will not be allowed for study participation.

Details of prior and concomitant medication use will be recorded in the source documentation and the electronic case report form (eCRF) as indicated in the SoA ([Appendix 1](#)).

5.9 Prohibited Medications

Receipt of systemic antiviral, antibacterial, antifungal, or antimycobacterial therapy within 7 days of Screening and for the duration of the study are prohibited. The use of the following

drugs and over-the-counter medications with equivalent efficacy will be prohibited from the first dose of study drug on Day 1 through Day 14 or early termination:

- Systemic antiviral (except study drug), antimicrobial*, and antifungal drugs**
- Antipyretics/analgesics (except acetaminophen)
- Antitussives/expectorants
- Combination cold remedies
- Antihistamines**
- Corticosteroids**
- Immunomodulators
- Traditional medicines used for respiratory infection (eg, Maoutou)
- Other investigational drugs

*Except for the treatment of complications of RSV infection suspected to be bacterial infection after Day 1.

**Dermal preparations permitted, but systemic use or topical application to the eyes, nose, or ears, or by inhalation are prohibited. However, inhaled corticosteroids used for treatment of COPD or asthma are permitted.

The use of St John's wort within 28 days prior to first dose of study drug and for the duration of the study is prohibited.

Additional prohibited medications are presented in [Section 3.2](#).

6. BLINDING

The study will be double-blinded, meaning that the subjects, investigators, and site staff will be blinded to treatment assignment until the completion of the study. All site staff will be blinded to treatment assignment except for the following individuals:

- Unblinded Enanta [REDACTED] statistician for purpose of generating and monitoring the randomization list
- Unblinded Enanta representatives not associated with the day-to-day conduct of the study as outlined in a separate DSMB charter
- Unblinded members of the DSMB for purposes of unblinded data review
- Unblinded Drug Supply Chain personnel for the purpose of monitoring drug supplies
- Enanta [REDACTED] Pharmacovigilance Group and Regulatory Affairs representatives when required to satisfy regulatory reporting requirements
- Bioanalytical laboratory for the purpose of measuring drug concentrations

6.1 Unblinding

At the initiation of the study, the study site will be instructed on the method for breaking the blind. The unblinding method will use the IWRS process.

Unblinding of individual subject treatment by the Investigator should be limited to medical emergencies or urgent clinical situations in which knowledge of the subject's study treatment is necessary for clinical management. In such cases, the Investigator must first attempt to contact the [REDACTED] Medical Monitor to discuss and agree to the need for unblinding. In situations which the Investigator has attempted and failed to contact the [REDACTED] Medical Monitor and/or the urgency of the case requires immediate action, investigators should use their best judgment, based on the nature and urgency of the clinical situation, and proceed with unblinding.

For unblinding, in the event that the local [REDACTED] Medical Monitor cannot be reached, sites at all locations should call the following 24/7 global medical coverage hotline: [REDACTED]

Once a subject's treatment assignment has been unblinded for a medical emergency or urgent clinical situation, the [REDACTED] Medical Monitor and study coordinator should be notified within 24 hours of unblinding of the treatment. Information relating to unblinding (eg, the reason, date) should be clearly recorded in the subject's study file. In addition, the Investigator should consider whether the clinical event that prompted unblinding should be considered an SAE, according to the regulatory definitions or criteria for SAEs, and if so, submit an SAE report as described in [Section 9.2](#).

The [REDACTED] group will also unblind any SAE reports in compliance with regulatory reporting requirements. In addition, Enanta Pharmaceuticals, Inc. may unblind individual subjects at any time for matters relating to safety concerns.

Note: Investigative sites will be provided country-specific toll-free telephone and fax numbers.

7. STUDY CONDUCT AND VISIT SCHEDULE

7.1 Study Site Visits

Details of assessments at each study site visit are presented in the SoA ([Appendix 1](#)). Also refer to the SPM. Study sites will be responsible for following up with subjects for any missed study site visits.

7.1.1 Screening Period on Day 1

Screening procedures will occur after the subject signs and dates an institutional review board (IRB)- or ethics committee (EC)-approved ICFs and provides authorization to use protected health information (see [Section 12.1.3](#)). The ICFs will be completed prior to conduct of any study-specific assessments.

At Screening (on Day 1), subjects will first review and sign the Rapid Viral Screen ICF prior to RSV and influenza screening. Subjects will undergo a rapid diagnostic screen for RSV and influenza virus using respiratory secretions obtained by nasal (or nasopharyngeal) swab collection; refer to the Laboratory Manual for details. Subjects whose swab sample test results positive for RSV and negative for influenza virus may proceed for further screening. Such subjects will be required to sign the full study ICF prior to performing any further study-specific assessments. After signing the full study ICF, subjects will undergo further screening procedures to determine study eligibility.

All study screening activities should be completed on Day 1. If any assessment is anticipated to fall outside of that window, then the Investigator should consult with the [REDACTED] Medical Monitor to determine if the subject can proceed. For subjects who sign the full study ICF and whose swab sample test results are positive for RSV and negative for influenza virus, the first screening activity should be to test subjects for severe acute respiratory syndrome coronavirus 2 (SARS-CoV-2) using a rapid molecular diagnostic test. Subjects will not be randomized until all screening activities that allow assessment of inclusion/exclusion criteria have been completed to the satisfaction of the Investigator, including the screening ECG and the screening urine pregnancy test.

All screening procedures are detailed in the SoA ([Appendix 1](#)).

7.1.2 Treatment Period (Days 1 to 5)

Study Site Visits (Days 1, 3, and 5):

Subjects who meet all inclusion criteria and none of the exclusion criteria to the satisfaction of the Investigator will be eligible to enter the study and will be randomized 1:1 to receive 800 mg of EDP-938 or placebo. Subject randomization will be stratified by the presence or absence of asthma/COPD.

Eligible subjects must complete the Day 1 biological sample collections (ie, blood, urine, and nasopharyngeal swab[s]) prior to receiving the first dose of EDP-938 or placebo. Day 1 blood

and urine samples will be sent to both local (expedited testing and reporting) and central laboratories. Nasopharyngeal swab(s) will be sent to the central laboratory only.

Eligible subjects will receive an electronic data capture handheld device (ERT[®] electronic clinical outcome assessment [eCOA] Handheld eDiary) to use for the duration of the study.

[REDACTED]

The device will also serve to alert the subject when it is time for study drug dosing. The subject will receive instruction on the proper use and care of the device, including the recording of the first dose, and the device should be brought to each study site visit. In case the subject is unable to complete any assessments or recordings into the device for technical reasons, the subject will also be provided with a paper diary(ies) as a back-up.

The subject will be instructed on the use of concomitant medications during the study, including the use of acetaminophen as the study-specific analgesic/antipyretic (see [Section 5.8](#) and [Section 5.9](#)).

Subjects will receive the first dose of study drug while at the study site. After the first dose, subjects will be instructed to take 800 mg of EDP-938 or placebo once daily at approximately the same time every day (± 1 hour) on each of the 4 subsequent days. The subject will also receive instruction on the appropriate storage and transport of study drug (see [Section 5.3](#)).

On Day 3 and Day 5 (EOT), subjects should bring their study drug with them as part of their study site visit [REDACTED] for drug accountability and for dosing of study drug on Day 5 as described in [Section 5.7](#). If a subject is unable to attend the Day 3 and/or Day 5 study site visit, a home visit by a study nurse may be arranged, if feasible; refer to the SPM for details. It is anticipated that every reasonable effort will be made to ensure that subjects return to the site for the Day 3 and Day 5 visits.

Subjects who discontinue treatment early (ie, prior to completing 5 days of dosing) should return to the study site within 24 hours and no more than 48 hours later to complete the EOS procedures.

All study assessments during the Treatment Period are detailed in the SoA ([Appendix 1](#)).

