7.1.3 Follow-up Period (Days 6 to 14)

Study Site Visits (Days 9 and 14):

Subjects should return to the study site for follow-up visits on Day 9 and Day 14 (EOS Visit) for post-treatment safety assessments. Visit assessments may be completed at the study site or by a study nurse via a home visit, if feasible; refer to the SPM for details.

Subjects who discontinue the study early (ie, prior to Day 14) should return to the study site within 24 hours and no more than 48 hours later to complete the EOS procedures.

All study assessments during the Follow-up Period are detailed in the SoA ([Appendix 1](#)).

Throughout the study, safety for each subject in each study period will be evaluated by assessment of clinical laboratory findings, physical examination findings (as applicable), vital sign measurements, pulse oximetry measurements (only for subjects with asthma or COPD), and AEs. Any subject with ongoing AEs/SAEs at the EOS Visit should be followed up until resolution of their AE/SAE or until the Investigator has determined that the event has stabilized as discussed in [Section 9.3](#).

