7.2 Subject Withdrawal/Early Termination

Subjects may withdraw from the study at any time at their own request, or subjects may be withdrawn at any time at the discretion of the Investigator or Enanta Pharmaceuticals, Inc. for safety, behavioral, or administrative reasons. However, the Investigator should consult with the [REDACTED] Medical Monitor where possible before prematurely removing a subject. For any subject who decides to withdraw from the study, the Investigator should inquire about the reason for withdrawal, request that the subject returns all unused investigational product(s), request that the subject returns for a final study site visit, if applicable, and follow up with the subject regarding any unresolved AEs. Although a subject may discontinue the study drug or the study early, every effort must be made for the subject to return to the site within 24 hours and no more than 48 hours later to complete the EOS procedures.

If a subject withdraws from the study and also withdraws consent for disclosure of future information, no further evaluations should be performed, and no additional data should be collected. Enanta Pharmaceuticals, Inc. may retain and continue to use any data collected before such withdrawal of consent.

Any randomized subjects who withdraw or are withdrawn from the study will not be replaced.

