7.2.2 Procedures for Early Discontinuation or Early Termination of Treatment

Subjects who prematurely discontinue treatment early and have received at least one dose of study drug should return to the site within 24 hours and no more than 48 hours later and undergo the EOS procedures per the SoA ([Appendix 1](#)). Any subject who withdraws with ongoing AEs/SAEs should be followed up until resolution of their AE(s) or until the Investigator has determined that the AE(s) has stabilized.

Site staff will attempt to contact any subject who does not return to the site for the EOS Visit at least three times using the subject's preferred method of communication, followed by a letter requiring delivery notification if the three attempts were unsuccessful. Any subject who still cannot be reached following those attempts will be considered lost to follow-up. These subjects will be included in the PK and safety analysis as indicated in [Section 11.3](#).

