14. APPENDICES

Appendix 1: Schedule of Assessments

Period Day	Screening	Treatment					Follow-up			
	1 Screening	1 Eligible Subjects ^a	2	3	4	5 (+1 d) EOT	6-8	9 (±1 d)	10- 13	14 (±1 d) EOS ^b
Study site visit	X			X ^c		X ^c		X ^c		X ^c
Informed consent form ^d	X									
RSV/influenza rapid diagnostic test ^e	X									
Inclusion/Exclusion criteria	X									
SARS-CoV-2 rapid diagnostic test ^f	X									
Demographics	X									
Medical history	X									
Smoking history	X									
Prior medications	X									
Vital sign measurements ^g	X					X				X
12-Lead ECG (resting)	X									
Physical examination ^h	X									
Weight, height, and BMI ⁱ	X									X
Pulse oximetry ^j	X					X				X
Frailty scale score (see SPM)	X									
Pregnancy test ^k	X (urine)	X (serum)								X (urine)
FSH ^l		X								
Clinical laboratory tests ^m		X				X				X
Randomization ⁿ		X								
eCOA Handheld eDiary ^o		X								X
RSV symptom diary eCOA ^p		X	X	X	X	X	X	X	X	X
		X	X	X	X	X	X	X	X	X
NP swab collection: confirmatory respiratory pathogen panel		X								
NP swab collection: RSV RNA quantitation of viral load		X		X		X		X		X
		X		X		X		X		X
RSV serology collection		X								X
		X								X
Study drug dosing ^s		X ^s	X	X	X	X ^s				
Study drug accountability ^t				X		X				X
PK sample collection		X ^u		X ^u		X ^u				X ^v
Concomitant medications ^w		X	X	X	X	X	X	X	X	X
Adverse events	X	X	X	X	X	X	X	X	X	X

Abbreviations: BMI = body mass index; COPD = chronic obstructive pulmonary disease; d = day; ECG = electrocardiogram; eCOA = electronic clinical outcome assessment; EOS = end-of-study; EOT = end-of-treatment; FSH = follicle-stimulating hormone; ICF = informed consent form; NP = nasopharyngeal; PK = pharmacokinetic; RSV = respiratory syncytial virus; SARS-CoV-2 = severe acute respiratory syndrome coronavirus 2; SPM = Study Procedures Manual. Note: Refer to the Laboratory Manual for sample collection and processing details.

- ^a Day 1 assessments to be performed in randomized subjects.
- ^b Subjects who discontinue treatment early (ie, prior to completing 5 days of dosing) or the study early (ie, prior to Day 14) should return to the study site within 24 hours and no more than 48 hours later to complete the EOS procedures.

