- ^l Follicle-stimulating hormone should be tested in postmenopausal females. Refer to [Section 8.4.2](#).
- ^m Clinical laboratory tests include chemistry, hematology, and urinalysis. See [Section 8.4](#) and [Table 2](#) for details regarding Day 1 sample collection and evaluations for the local and central laboratory(ies).
- ⁿ Subjects who meet all inclusion criteria and none of the exclusion criteria to the satisfaction of the Investigator, including the screening ECG and the screening urine pregnancy test, will be eligible to enter the study and will be randomized 1:1 to receive 800 mg of EDP-938 or placebo. Subject randomization will be stratified by the presence or absence of asthma/COPD.
- ^o Eligible subjects will receive an electronic data capture handheld device (ERT[®] eCOA Handheld eDiary) on Day 1 and will return the device to the study site at the EOS Visit. Refer to [Section 7.1.2](#) for additional details.
- ^p The RSV symptom diary will be self-completed by subjects twice daily at the same times each day ± 2 hours as an eCOA. If a subject plans to take acetaminophen within 2 hours of the scheduled RSV symptom diary completion, then the RSV symptom diary should be completed immediately before the subject takes acetaminophen or 4 hours after taking acetaminophen.
- ^q [REDACTED]
- ^r [REDACTED]
- ^s Study drug (EDP-938 or placebo) should be administered at the study site on Days 1 and 5. On Day 5, the study site visit should be scheduled close to the time that the subject normally takes the study drug so that dosing can occur at the site. From Day 1, subjects will electronically record the time and date that each dose is taken. See [Section 5.7](#) for additional dosing details.
- ^t Study drug accountability by tablet count and review of the electronic dosing record completed by the subjects.
- ^u On Day 1, collect one postdose plasma PK sample, at least 1 hour after dosing or right before the subject leaves the site, whichever is later. On Day 3, collect one plasma PK sample at the same approximate time as that of the NP swab collection. On Day 5, collect one predose PK sample. If the subject takes the study drug prior to the study site visit, a PK sample should be taken at the same approximate time as that of the NP swab collection. See [Section 5.7](#) and [Section 8.6](#) for additional details.

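### Subjects who only stop study drug are sent to the same early EOS visit as those who leave the study, and the plan does not say whether diary and swabs then continue to Day 14

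*Protocol*

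**What the plan says.** The specific rules put both groups on one path.

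- Protocol 7.1.2, on stopping treatment: "Subjects who discontinue treatment early (ie, prior to completing 5 days of dosing) should return to the study site within 24 hours", and at most 48 hours later, for the EOS procedures. Protocol 7.1.3 gives the same instruction for leaving the study.
- Protocol 7.2 joins the two: "Although a subject may discontinue the study drug or the study early, every effort must be made for the subject to return".
- Protocol 7.2.2: "Subjects who prematurely discontinue treatment early and have received at least one dose of study drug should return to the site" on the same timing. It names no later visits.
- Footnote b of the Schedule of Assessments (SoA): "Subjects who discontinue treatment early (ie, prior to completing 5 days of dosing) or the study early (ie, prior to Day 14) should return".
- Protocol 5.7.2 names this occasion when it lists where study drug is brought back: "EOS Visit (for subjects who discontinue study drug or the study early".
- SoA footnote o, on the eDiary: subjects "will return the device to the study site at the EOS Visit".

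The general text points the other way.

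- Protocol 7.1.2 issues the eDiary "to use for the duration of the study".
- Protocol 7.1.3: "Subjects should return to the study site for follow-up visits on Day 9 and Day 14 (EOS Visit".
- SAP 5.2 runs the diary twice daily through Day 14, and Protocol 11.6.2 schedules viral load on Days 1, 3, 5, 9 and 14.

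Neither document, as supplied, says which set governs once a subject who only stopped drug has had the early visit.

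**The concern.** The primary endpoint is TSS AUC from Day 1 through Day 14. If a site treats the early visit as the end of data collection, symptom scores and swabs are lost because of a visit rule, not because the subject is unwilling to give them.

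These subjects are not dropped from the analysis. SAP 3.5 keeps every randomized, dosed, central RT-PCR positive subject in the mITT population. SAP 3.14.1 needs only two scores for an AUC and multiplies the result by 14/t_last. SAP 3.14.2 does the same for viral load. The unobserved days are therefore filled with the early-illness average.

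SAP 3.3 points to 3.14.1.1 for missing efficacy data, but 3.14.1.1 contains no imputation analysis. Protocol 11.6.2 does plan multiple imputation, but that would model data that could have been observed. The per-protocol repeat requires completed treatment, so it omits these subjects and cannot test the problem.

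**Working it through.** **1. One path or two?** Protocol 11.4 and SAP 3.7 count stopping drug and leaving the study separately, so the plan recognises two events. The visit rules give them one route. The PK text (Protocol 8.6, SoA footnote v) asks for an EOS sample only from subjects who leave the study before the last dose, which reads as if stopping dosing were leaving the study. The passages do not settle the question.

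**2. The plan's own figure.** Inputs (Protocol 11.2): means 500 and 225, SDs 450 and 200, 27 per group. Two-sided alpha of 0.05 is from Protocol 11.1. For the unequal-variance t-test the noncentrality is 275 / sqrt((450² + 200²)/27) = 275/94.8 = 2.90, and power is 80.6%. The stated 80% reproduces. Dropout: 27/0.80 = 33.75, so 34, close to the stated 35 or so.

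**3. Effect of the scaling on one subject.** Ratio = [AUC(0,t) × 14/t] / AUC(0,14), with t the time in days from first dose to the last diary. The documents give no symptom curve, so these are assumptions:

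- A: TSS falls exponentially from baseline with half-life h. Ratio = (14/t) × (1 − 2^(−t/h)) / (1 − 2^(−14/h)).
- B: TSS rises linearly from 0.5 to 1 at day p, then falls with half-life h.

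| Curve | t=1 | t=2 | t=3 | t=4 | t=5 |
|---|---|---|---|---|---|
| A, h=2 | 4.13 | 3.53 | 3.04 | 2.65 | 2.32 |
| A, h=3 | 3.01 | 2.70 | 2.43 | 2.20 | 2.00 |
| A, h=5 | 2.12 | 1.98 | 1.85 | 1.74 | 1.63 |
| B, p=2, h=3 | 1.57 | 1.89 | 2.01 | 1.95 | 1.85 |
| B, p=2, h=5 | 1.19 | 1.43 | 1.55 | 1.55 | 1.51 |
| B, p=3, h=3 | 1.31 | 1.50 | 1.68 | 1.76 | 1.73 |
| B, p=3, h=5 | 1.03 | 1.18 | 1.33 | 1.41 | 1.42 |
| B, p=4, h=3 | 1.14 | 1.27 | 1.40 | 1.52 | 1.58 |
| B, p=4, h=5 | 0.94 | 1.04 | 1.14 | 1.25 | 1.31 |

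Example, last row, t=1: AUC(0,1) = 0.5625 and AUC(0,14) = 3 + (5/ln 2)(1 − 2^(−2)) = 8.41, so the ratio is 14 × 0.5625/8.41 = 0.94. A flat course gives 1.0. A steeper rise (5 at day 0, 18 at day 3, linear to 0 at day 12) gives 0.87 at t=1. Days 1 and 2 belong in the range: someone who stops after the first dose and returns in 24 to 48 hours has a last diary about then.

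**4. Effect on an arm mean.** Assume one such subject in 35, whose full AUC would equal the arm mean. Shift = (ratio − 1)/35: (0.94 − 1)/35 = −0.2% and (4.13 − 1)/35 = +8.9%.

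**5. Against sampling error.** Planning standard error as a share of the mean at 35 per arm: 450/√35/500 = 15.2% for placebo and 200/√35/225 = 15.0% for EDP-938. The largest shift is about 8.9/15 = 0.6 of a standard error. I use percentages because the SAP scale tops out at 39 × 14 = 546 score-days, and the documents do not give the units of the planning mean of 500.

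**The case against.** **Silence is not a stop rule.** A reader might infer that the protocol ends collection when drug stops. It does not say so. It requires the EOS procedures, places the EOS Visit at Day 14 (Protocol 4 and 7.1.3), and runs the diary and swab rows to Day 14 without an exception. SAP 3.1 ties completion to the last planned visit. The Protocol 5.7.2 parenthesis concerns bringing back study drug, and the Study Procedures Manual, not supplied, may address the matter. This stands to the extent that a site could reasonably stop, not that it would. The device-return rule still makes stopping the natural reading of the specific text.

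**Early exit may be deliberate.** The PK text supports this. If so, the plan gives up primary-endpoint data from subjects it keeps in the primary analysis, and the general Day 14 text should say so. The passages need reconciling either way.

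**The effect may be nil.** This stands. A reader might also take the single drug discontinuation reported in Protocol 1.5 over the roughly 300 exposed in Protocol 4.2.1 as a rate for this trial. The documents do not support that: those subjects received EDP-938, some as a single dose, in healthy-volunteer or challenge studies, while half of this trial takes placebo. The 20% planning dropout does not separate stoppers from leavers.

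**The harm comes from the scaling.** Partly right. The fix leaves 14/t_last in place and does nothing for leavers. For subjects who stay, observed scores remove the need to extrapolate.

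**Conclusion.** The point holds as an unresolved conflict between specific and general rules that can cost primary-endpoint data. It is worth correcting because the remedy is cheap and lost diary days cannot be recovered.

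On the assumed declining or rise-then-decline curves, one affected subject in 35 shifts that arm's mean by about −0.2% to +8.9%, against a planning standard error of about 15%. The range depends on the curves: nothing happens with a flat course, and a steeper early rise goes slightly lower. The number of drug-only stoppers is unknown and may be zero.

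A reader might infer that the scaling favours one arm. The documents do not support that, since the direction depends on which arm has more such subjects and when they stop.

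A secondary gap: SAP 3.6 assigns viral load, laboratory tests and vital signs by nominal visit and does not say how an early EOS visit is labelled. A reader might take this as affecting descriptive tables only. It also reaches the Cochran-Mantel-Haenszel test at each visit day in SAP 3.14.2. It does not touch either AUC, which use actual times.

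**What to change.** In Protocol 5.7.2, 7.1.2, 7.2 and 7.2.2, SoA footnotes b and o, the protocol summary, and SAP 5.1 footnotes b and o, separate stopping drug from leaving the study:

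- Keep the 24 to 48 hour visit for both groups.
- Subjects who stop drug but do not withdraw from the study keep the eDiary, continue twice-daily entries and the remaining scheduled swabs through Day 14, and return the device at their actual last visit. Assessments done at the early visit need not all be repeated.
- Subjects who leave the study follow the current text.

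In SAP 3.6, label early-termination assessments separately, so that they do not enter the Day 14 summaries or the Day 14 Cochran-Mantel-Haenszel test as Day 14 data.

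Cost: a short protocol amendment and a few SAP lines. The device, visits and swabs are already planned for every subject. The downside is diary and visit burden for people who have stopped drug. When or why drug is stopped is unchanged, and the change does not help with subjects who leave the study.
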